3.4.4.4.1 Rash with Hyperkeratosis / Keratoacanthoma / Squamous Cell Carcinoma of the Skin

Dermatological consults will be requested on a case-by-case basis as needed with potential biopsy of suspicious skin lesions.

3.4.4.4.2 Suggested Evaluation of Suspected Bleeding or Hemorrhage Events and Treatment Modification

For anemia or hemorrhage events assessed as treatment-related, items queried may include but are not limited to detailed relevant past medical and treatment history, bruising tendency, history of blood transfusions and/or dependency, and a request for an updated participant history including details such as concomitant medications, all laboratory data, updated dosing information and recent tumor evaluation scans.

In this protocol, anemia may be due to M7824 (documented in 29% of patients based on pooled safety analysis set from a total of 765 participants, refer to IBv7) and/or SX-682. For M7824 anemia is an AESI and important identified risk (see Investigators' Brochure). Notably, there are many reasons for hemorrhage and/or anemia in patients with advanced cancer, and Hb level of at least 9 g/dL is required for this study. A thorough investigation of new anemia cases of unspecified etiology is recommended:

- Participants must enter the study with Hgb values at least 9 g/dL and baseline anemia evaluation is conducted per **recommendations below**.
- **Consider hematology consult for severe and or refractory anemias.**

- All relevant hematologic testing for treatment related anemias should be done prior to blood transfusion, if clinically feasible.
- Transfusion should be performed at the discretion of the investigator, based on clinical assessment and considered when participant experiences significant anemia.
- Guidance for evaluation of baseline anemia or suspected treatment-related anemias is provided below. Investigators may consider the following laboratory evaluations in participants with anemia.
 - Hb and CBC with differential (e.g. MCV, RDW, ANC, hematocrit, reticulocytes counts)
 - Peripheral blood smear for cell morphological assessment
 - Complete metabolic panel including liver panel-LFTs, bilirubin, LDH, renal function, and serum folate, B12 values and other chemistries
 - Coagulation factors (PT, PTT, INR)
 - Urinalysis including culture
 - Iron panel (TIBC, ferritin, Fe)
- Discuss further management with Principal Investigator for clinically significant treatment related anemias.

Multiple protocols using M7824, several mucosal bleeding events ranging from low grade gingival bleeding and epistaxis to more serious hemoptysis, GI bleeding and hematuria have been observed. Some of these events can be attributed to bleeding events related to cancer directly and others bleeding events can be attributed to an inflammatory process (e.g. colitis) which is a known toxicity of anti-PD-L1 agents including M7824. However, there remains the possibility that M7824 may increase the overall risk of bleeding in ways that may not be directly related to direct tumor bleeding or inflammatory bleeding events described with checkpoint inhibitors like M7824. However, there is no evidence of a negative effect on coagulation or platelet number or function. It is hypothesized that this possible increased mucosal bleeding risk may be due to the known mucoprotective effects of TGF β . Accordingly, participants will be closely monitored for mucosal bleeding (e.g., gum bleeding, nose bleeds, coughing up blood, blood in their urine, or blood in the stool).

3.5 STUDY CALENDAR

	Screening	Baseline ¹	Lead-In (Days -14L to -1L)	Cycles ² Cycle=28 (-1/+ 3) days		EOT ⁶	Safety FU ⁷	Long Term FU ⁸
				Day 1	Day 15			
SX-682 ³			X	X	X			
M7824 ⁴				X	X			
MVA-BN-CV301 (Cycle 1 only) ⁵				X	X			
FPV-CV301(Cycle 2 onward) ⁵				X				
Medical History	X							
Height	X	X						
ECOG	X	X				X		
Clinical Assessment - physical exam, vital signs ¹⁸ , weight	X	X		X	X	X	X	
HIV, HCV, HBV viral load by PCR	X							
CD4	X							
EKG ⁹	X	X		X	X	X	X	
CBC w/differential with platelets	X	X		X	X	X	X	

	Screening	Baseline ¹	Lead-In (Days -14L to -1L)	Cycles ² Cycle=28 (-1/+ 3) days		EOT ⁶	Safety FU ⁷	Long Term FU ⁸
				Day 1	Day 15			
Biochemical profile ¹⁰	X	X		X	X	X	X	
Lymphocyte profiling (TBNK), TSH, Free T4, lipase, amylase, urinalysis ¹¹	X	X		X				
Pregnancy testing in women of childbearing potential ¹²	X	X		X		X		
PT/PTT/INR ¹¹	X	X		X				
Flexible clinic-based pharyngolaryngoscopy (HNSCC only) if clinically indicated	X	X		as needed				
Tumor evaluation (CT Scan / MRI, if clinically indicated) ¹³	X			X				X
A brain CT / MRI scan (if clinically indicated) ¹⁴	X							
Nuclear bone scan (if clinically indicated)	X							
Concomitant medications	X	X		X	X	X	X	
Adverse event evaluation				X	X	X	X	
Baseline signs and symptoms		X						

	Screening	Baseline ¹	Lead-In (Days -14L to -1L)	Cycles ² Cycle=28 (-1/+ 3) days		EOT ⁶	Safety FU ⁷	Long Term FU ⁸
				Day 1	Day 15			
Tumor biopsy (optional) ¹⁵		X		X		X (at disease progression)		
Research blood ¹⁶		See Table 9 (Arm 1), Table 10 (Arm 2), and Table 11 (Arm 3)						
Telephone or E-mail Follow Up								X
Collection of archival tumor samples for research if available		X						
Diet Order (may be ordered during visits if clinically indicated)			X	X	X			
Confirmation of disease ¹⁷	X							

¹Baseline evaluations do not need to be repeated if performed at screening within 7 days of any first drug administration. If treatment does not start within 28 days after enrollment (or if specific longer), screening evaluations will be repeated.

² Participants will be seen in clinic every 2 weeks while on treatment. If treatment is being held, clinic visits may be missed and the associated labs will be deferred per the discretion of the PI. Due to COVID-19 pandemic, outside of the DLT period, if the participant is not able to return to the NIH CC for treatment/follow-up, remote visits will be conducted in compliance with NIH guidelines and FDA regulations. A participant may be referred to their local provider or asked to come to the NIH CC for an in-person assessment, if clinically indicated, and at the discretion of the PI. In the case of any visits with participants' local providers, records will be obtained.

³ Arm 1: during Lead-In only. Arms 2 and 3: during Lead-In (Arm 2 only) and every day of every cycle. See [Table 8](#)

⁴ On days 1 and 15 of every cycle. Can be -1/+3 days due to holidays, inclement weather, conflicts, or similar reasons except where explicitly noted elsewhere. M7824 drug administrations should not be given less than 11 days apart. See [Table 8](#)

⁵ MVA-BN-CV301 will be given on days 1 and 15 of Cycle 1. FPV-CV301 will be given Day 1 of Cycles 2 through 5 then Day 1 of Cycle 8 and Cycle 11. Can be -1/+3 days due to holidays, inclement weather, conflicts, or similar reasons except where explicitly noted elsewhere. CV301 administrations should not be given less than 11 days apart. See **Table 8**

⁶ EOT – End of treatment visit: Where feasible, on the day of or within 30 days of the decision to discontinue treatment prematurely before completion of one year of treatment. Does not need to be completed if drug is withheld after one year of treatment. Research labs will be collected if feasible. Participants continuing to experience toxicity at the off-treatment visit will be contacted for additional assessments until the toxicity has resolved or is deemed irreversible. Participants must remain on the study to have additional assessments completed

⁷ 30 days (+/- 7 days) after last treatment. If subjects are not willing to come to NIH to FU visit, they will be contacted by phone to assess adverse events. Does not need to be repeated if EOT performed within this time frame.

⁸ Participants who are taken off treatment for reasons other than disease progression, will be invited for optional imaging studies every 3 months (+/- 2 weeks) until they experience PD in order to assess PFS. If participants unable to come, participants will be followed by phone or email and outside images will be requested. Participants who opt out of these scans will have their data censored in data analysis at the time they become unfollowable for PFS. After progression and 30 days Safety Follow up visit, participants will be followed by phone or email for long-term clinical outcomes, and further tumor therapy every year for 2 years.

⁹ EKGs will be done in triplicate on screening, before SX-682 administration at baseline and then every two weeks until cycle 6, at EOT and at the safety FU visit.

¹⁰ Biochemical profile: sodium, potassium, magnesium, phosphorus, chloride, bicarbonate, calcium, glucose, BUN, creatinine, ALT, AST, alkaline phosphatase, total protein, albumin, and total and direct bilirubin.

¹¹ Performed every 8 weeks: Lymphocyte panel (TBNK), TSH, Free T4, lipase, amylase, urinalysis, PT/PTT/INR, unless there is a clinical concern that warrants evaluation on a more frequent basis

¹² For women of childbearing potential at screening and baseline serum pregnancy test must be performed, but on day 1 of each cycle and EOT, urine pregnancy test can also be used.

¹³ In Arms 1 and 2, the first restaging will occur 6 weeks after starting treatment (+/- 1 week) and then every eight weeks (+/- 1 week). In Arm 3, restaging will occur every eight weeks (+/- 1 week). In the event of a PR or CR tumor imaging assessments may be performed every 3 months (+/- 2 weeks) at the discretion of the investigator. Tumor assessment should be continued beyond end of treatment in participants who have not experienced PD until they experience PD in order to assess PFS. In addition to a baseline scan, confirmatory scans can also be obtained 4 to 8 weeks following initial documentation of objective response per the discretion of the primary investigator. MRI of chest, abdomen and pelvis (if participant has contradiction to CT).

¹⁴ Brain CT/MRI if there is a history of prior CNS metastasis or there is a concern for CNS involvement.

¹⁵ Optional biopsies at baseline and as close as logistically feasible to first imaging restaging (+/- 1 week if possible). Optional biopsy also at time of progression. In addition, tissue collected during unscheduled procedures may also be collected for research purposes.

¹⁶ Where feasible, research blood for all study assessments will be collected as per **Table 9**, **Table 10**, and **Table 11** below. The exact collection time for PK samples will be recorded

¹⁷ See Section [2.2.2](#)

¹⁸ Arms 1 & 2: Day -14, SX-682 oral administration; collect full set of vital signs pre dose and (180 minutes) 3 hours post dose at the time of last PK blood collection.

All 3 Arms: All cycles with CV301 & M7824 administration; collect a full set of vital signs pre CV301 vaccine administration and prior to start of M7824 infusion. During the M7824 infusion, collect a full set of vital signs every 30 minutes and at the end of the 60 minute observation period, for C1D1 and C1D15 doses. For the 3rd M7824 dose, C2D1 and all subsequent M7824 doses, the observation period is 30 minutes, a full set of vital signs will be collected at that time.

Table 8: Study Drug Administration

Arm 1:

Lead-In (days)	Cycle 1		Cycle 2 until Progression	
Days -14L to -1L	C1D1	C1D15	CxD1	CxD15
SX-682				
	M7824	M7824	M7824	M7824
	MVA-BN-CV301	MVA-BN-CV301	FPV-CV301*	

*Given every cycle for 4 cycles, then every 3 cycles for 2 additional doses (total of 1 year of vaccines).

Arm 2:

Lead-In (days)	Cycle 1		Cycle 2 until Progression	
Days -14L to -1L	C1D1	C1D15	CxD1	CxD15
SX-682	SX-682 → → → → → → → → → → → → → →			
	M7824	M7824	M7824	M7824
	MVA-BN-CV301	MVA-BN-CV301	FPV-CV301*	

*Given every cycle for 4 cycles, then every 3 cycles for 2 additional doses (total of 1 year of vaccines).

Arm 3:

Cycle 1		Cycle 2 until Progression	
C1D1	C1D15	CxD1	CxD15
SX-682 Continuous			
M7824	M7824	M7824	M7824
MVA-BN-CV301	MVA-BN-CV301	FPV-CV301*	

*Given every cycle for 4 cycles, then every 3 cycles for 2 additional doses (total of 1 year of vaccines).

Table 9 Arm 1 Research Blood Draws

Cycle (Day)	Time	SX-682	M7824		Immune and Other Analyses		
			PK	ADA	Soluble Factors	Immune phenotyping/ RNA analysis, Antigen-specific response, T-cell clonality	CTCs
Lead-In (-14L)	predose	X			X	X	X
	30 minutes	X					
	60 minutes	X					
	120 minutes	X					
	180 minutes	X					
	< 6 hours of 2 nd dose	X					
Lead-In (-7L) *	predose	X					

Cycle (Day)	Time	SX-682	M7824		Immune and Other Analyses		
			PK	PK	ADA	Soluble Factors	Immune phenotyping/ RNA analysis, Antigen-specific response, T-cell clonality
	30 minutes	X					
Cycle 1 (1)	predose	X	X	X	X	X	X
	End of Infusion (EOI)	X	X				
Cycle 1 (15)		X			X	X	
Cycle 2 (1)	predose	X			X	X	X
Cycle 3 (1)**	predose	X	X**	X**	X	X	
EOT			X	X	X	X	

*Lead-In, Day -14L labs only for Cohort 1, Arm 1 (Sequential Dose Escalation).

**The last M7824 PK/ADA timepoint should be Cycle 3, Day 1 predose or EOT, whichever comes first.

Table 10: Arm 2 Research Blood Draws

Cycle (Day)	Time	SX-682	M7824		Immune and Other Analyses		
			PK	PK	ADA	Soluble Factors	Immune phenotyping/ RNA analysis, Antigen-specific response, T-cell clonality

Cycle (Day)	Time	SX-682	M7824		Immune and Other Analyses			
			PK	PK	ADA	Soluble Factors	Immune phenotyping/ RNA analysis, Antigen-specific response, T-cell clonality	CTCs
Lead-In (-14L)	predose		X	Not given until C1D1	Not given until C1D1	X	X	X
Cycle 1 (1)	predose	X	X	X		X	X	
	EOI	X	X					
Cycle 1 (15)		X			X		X	
Cycle 2 (1)	predose	X	X	X	X		X	
Cycle 3 (1)*	predose	X	X*	X*	X		X	
EOT		X	X	X	X		X	

*The last M7824 PK/ADA timepoint should be Cycle 3, Day 1 predose or EOT, whichever comes first.

Table 11: Arm 3 Research Blood Draws

Cycle (Day)	Time	Immune and Other Analyses			
		Soluble Factors	Immune phenotyping/ RNA analysis, Antigen-specific response, T-cell clonality	CfDNA	CTCs

Cycle (Day)	Time	Immune and Other Analyses			
		Soluble Factors	Immune phenotyping/ RNA analysis, Antigen-specific response, T-cell clonality	CfDNA	CTCs
Cycle 1 (1)	predose	X	X	X	X
Cycle 1 (15)	predose	X	X	X	
Cycle 2 (1)	predose	X	X	X	X
Cycle 3 (1)	predose	X	X	X	
EOT		X	X	X	

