1. INTRODUCTION

1.1 STUDY OBJECTIVES

1.1.1 Primary Objectives:

- Arm 1 (Sequential Dose Escalation):
 - To evaluate the safety and tolerability of single agent SX-682.
 - To determine the MTD of SX-682 followed by M7824 and CV301 vaccines in participants with advanced or metastatic solid tumors. If the MTD is not reached the study will be focused to describe the safety and tolerability of SX-682 followed by M7824 and CV301 vaccines.
- Arm 2 (Combination Dose Escalation):
 - To determine the RP2D of SX-682 with M7824 and CV301 vaccines in participants with advanced or metastatic solid tumors. If the MTD is not reached the study will be focused to describe the safety and tolerability of the drug combination.
- Arm 3 (Expansion):
 - To evaluate preliminary efficacy based on objective response rate (ORR), in each disease cohort separately.

1.1.2 Secondary Objectives:

- Arms 1 and 2 (Dose Escalations):
 - To characterize the PK/PD profile of SX-682 as a single agent and in combination.
- All Arms:
 - To evaluate preliminary efficacy: disease control rate (DCR; CR+PR+SD) and progression-free survival (PFS) using RECIST1.1.

[figure not shown]
1.1.3 Exploratory Objectives (may be performed on selected participants if there are adequate samples.):

- All Arms:
 - To evaluate the effect on immune cell subsets and soluble factors in peripheral blood.
 - To evaluate the effect on cytokine levels (IL-8, IL-6 and others) in peripheral blood.
 - To evaluate the effect on T cell clonality in peripheral blood and tumor samples.
 - To evaluate the effect on antigen-specific T cells responses to CEA, MUC1 and the cascade antigen brachyury in peripheral blood.
 - To evaluate the effect on antigen-specific T cell responses to CEA, MUC1 and the cascade antigen brachyury in tumor biopsies.

- To evaluate the presence of lymphocytic and myeloid cell infiltrates and other tumor markers as well as to evaluate RNA expression for IL-8, TGF- β and other soluble factors in tumor biopsies.
- To evaluate clinical responses (ORR, and DCR) per iRECIST
- To evaluate M7824 PK profile in this drug combination
- To evaluate ADA in this drug combination
- To evaluate long term (2 years after completion of treatment) clinical outcomes
- To evaluate circulating tumor cells (CTCs)
- In Arms 1 and 2 (Dose-Escalation Cohort), the following are the parameters will be evaluated, separately per dose level:
 - To evaluate ORR per RECISTv1.1

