3.1.2 Dose Escalation Common Rules

Starting dose of SX-682 will be 25 mg by mouth twice daily (50 mg total daily dose).

The first 3 participants enrolled on a given dose level of Arms 1 and 2 will be observed for DLT. If no DLT in those 3 participants, the next dose level will open. If DLT(s) occur, see **Table 5**.

There will be an interval of at least 28 days between enrolling the last participant on a given dose level and enrolling a participant on the next dose level in Arms 1 and 2, in order to assess for DLTs.

Subjects who do not complete the DLT observation period for reasons other than a DLT will be replaced and not included in the evaluation.

Participants will be eligible for the DLT evaluation if at least ≥ 85 percent of SX-682 scheduled doses were taken and 100% of scheduled doses of M7824 or CV301 were administered within the DLT period.

In case of DLT, DLT will be documented and participant, per PI discretion, may continue study treatment if toxicity could be managed by interruption of the dose of study treatment or dose reductions (See section **3.4**). Participant, once having DLT, will not be used for DLT evaluation on another dose level if treated on a lower dose level.

Any of the trial drugs may be discontinued for toxicity per the discretion of the primary investigator if it is felt that the toxicity can be directly linked to a specific drug or drugs. Per PI

discretion participant can continue treatment with 2 other drugs. However, if 2 drugs or more must be discontinued, the participant will be taken off treatment.

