3.3.2 SX-682

SX-682 will be given orally at designated dose twice a day every day. SX-682 is available as a 25 mg and a 100 mg tablet. If necessary, the 100 mg tablets can be cut in half using a pill splitter; the tablets are pre-scored for this purpose. The tablets are not to be crushed, chewed, or dissolved before swallowing.

SX-682 should be taken at approximately the same times each day. Participants should take SX-682 with water once in the morning (suggested between 6-9 am) and once in the evening (suggested between 6-9 pm). For two hours before and one hour after the dose, the participant's diet should be limited to clear liquids only (no solid foods). Doses should be taken within 2 hours of the scheduled time.

In case of a missed dose (more than 2 hours late) or vomiting after taking SX-682, participants will be instructed not to make up the missed dose.

Up to 15% of scheduled doses of SX-682 can be missed per cycle unless directed by PI/AI to hold additional doses of SX-682 during a planned cycle.

Participants will complete and return Participant's Diary ([Appendix C](#)), which will be reviewed by research staff at the end of each cycle.

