3.4.2 SX-682

If any SX-682 related AE observed is grade > 2 (except for electrolyte abnormalities that can be easily replenished or other lab abnormalities that have no clinical consequence or can be easily medically managed with minimal risk to the participant), treatment should be delayed by 1 week (except for hyperbilirubinemia where drug will be held for grade 2) – and up to 4 consecutive weeks. If, with a delay of up to 4 weeks, the treatment related AE resolves, then SX-682 can be resumed at the same dose level or at a lower dose level per the PI discretion.

If, after 4 weeks of delay, all treatment related AEs have still not resolved (to grade ≤ 1), then any further treatment with SX-682 should be delayed until AEs are resolved (to grade ≤ 1), and then reduced by one dose level at the time of reinitiating.

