10.4.5 Safety Analyses

The fraction of participants who experience a toxicity, by grade and type of toxicity, will be tabulated per dose level (both single agent and combination of agents) during the Arms 1 and 2 portion of the trial. Participants who take one dose or more of SX-682 will be evaluable for safety.

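### Arm 1 schedules no blood count or chemistry while SX-682 is being taken, so the grade 2 bilirubin hold has no scheduled test to trigger it

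*Combined protocol and SAP*

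**What the plan says.** **Dosing.** Sections 3.1.3 and 3.3.2 give Arm 1 SX-682 twice daily on Days -14L to -1L, followed by M7824 and CV301 from C1D1. Footnote 3 of the Study Calendar agrees: "Arm 1: during Lead-In only".

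**Laboratory schedule.** In section 3.5 the row "CBC w/differential with platelets" and the biochemical profile row are marked at screening, baseline, Days 1 and 15 of each cycle, end of treatment and safety follow-up. Both are blank in the lead-in column, where only SX-682 and the diet order are marked. Bilirubin belongs to the biochemical profile (footnote 10). Baseline tests come before the first dose (section 2.4).

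**Hold rule.** Section 3.4.2 delays SX-682 for related events above grade 2, with exceptions for laboratory changes of no clinical consequence. It sets a lower threshold for bilirubin: "treatment should be delayed by 1 week (except for hyperbilirubinemia where drug will be held for grade 2". Nothing in that section treats Arm 1 differently.

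**Existing mid-lead-in draw.** Table 9 has Arm 1 blood for SX-682 pharmacokinetics at Day -7L, before the dose and 30 minutes after it. Footnote 16 makes research blood conditional on feasibility. The asterisk on the Day -7L row leads to a note about a different day ("Day -14L labs only for Cohort 1, Arm 1 (Sequential Dose Escalation"), which may be only a slip of layout.

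**Evaluability.** Section 3.1.2 admits a participant to the DLT evaluation if at least "85 percent of SX-682 scheduled doses were taken". Section 3.3.2 is looser about directed holds: "Up to 15% of scheduled doses of SX-682 can be missed per cycle unless directed by PI/AI to hold additional doses". Section 10.4.5 keeps everyone in the safety tabulation: "Participants who take one dose or more of SX-682 will be evaluable for safety".

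**Objective.** The first Arm 1 primary objective in section 1.1.1 is "To evaluate the safety and tolerability of single agent SX-682".

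**The concern.** The protocol treats bilirubin as the one SX-682 toxicity that warrants stopping at a lower grade. A rise in bilirubin can be silent, so a symptom diary or a team discussion will not reveal it; someone has to draw blood. In Arm 1 the whole SX-682 course fits between two scheduled panels. By the time the second is read, there is nominally no drug left to withhold.

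Two things are at stake. The first is participant safety: a stopping rule written into the protocol depends, in this arm, on a test nobody has scheduled. The margin can also be thin. Section 2.1.1 admits a total bilirubin up to just under 1.5 times the upper limit of normal, and Table 7 starts grade 2 just above that value. The second is information: the laboratory side of the single-agent safety objective rests on one post-dose time point, so a change that rises and settles within the two weeks would not be seen.

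**Working it through.** No sample-size formula applies. The check is a count on the calendar, with Day -14L taken as day 1.

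**Inputs:** lead-in Days -14L to -1L (3.1.3); two doses a day (3.3.2); panels at baseline, C1D1 and C1D15 (3.5); cycle window -1/+3 days (3.5); Day -7L draw (Table 9); 85% rule (3.1.2); 28-day DLT window (3.1.1); participant numbers (10.2).

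**Length of exposure.** Days -14L to -1L are 14 days, which matches the stated 2 weeks. Scheduled doses: 14 x 2 = 28.

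**Panels between first and last dose.** Baseline comes before day 1, and C1D1 is nominally day 15. Count: 0. With the -1/+3 window, C1D1 falls on days 14 to 18.

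**Doses a hold could still spare:**

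| First result available | Doses already taken | Doses left of 28 |
|---|---|---|
| C1D1 as planned | 28 | 0 |
| C1D1 one day early (Day -1L) | 26 to 27 | 1 to 2 |
| Day -7L, same-day result | 7 x 2 + 1 = 15 | 13 (46.4%) |
| Day -7L, next-day result | 16 | 12 (42.9%) |

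The Day -7L morning dose is counted as taken because the 30-minute pharmacokinetic sample needs it. Time from first dose to first scheduled value falls from 14 elapsed days to 7.

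**Position in the DLT window.** C1D1 is 14 days and C1D15 is 14 + 14 = 28 days after the first dose. Both are nominally inside the 28-day window, the second at its edge.

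**Effect of a hold on DLT evaluability.** 0.85 x 28 = 23.8, so 24 doses are needed and at most 4 may be missed. A participant held after the Day -7L morning dose has taken 15/28 = 53.6% (16/28 = 57.1% with a next-day result). Both are below 85%.

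**Replacements.** The documents give no rate of grade 2 hyperbilirubinemia. Assuming 2% to 10% for illustration, and 9 to 30 Arm 1 participants: 9 x 0.02 = 0.18 at the low end and 30 x 0.10 = 3.0 at the high end. This counts bilirubin holds only; holds for other laboratory events would add to it. The places available are 105 - (60 + 21 + 16) = 105 - 97 = 8, shared by the whole trial.

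**The case against.** The strongest reply is that panels run every two weeks throughout the trial, and Day -14L to C1D1 is that same interval. Section 3.4.2 is written for all arms, and its language of delay and later resumption suits continuous dosing better than a fixed two-week course; a one-week delay from Day -7L would use up what is left of the lead-in. Investigators may hold any drug at their discretion (3.4.1), the team reviews every treated participant weekly (7.5.1), and unscheduled tests are not barred. The drug-risk background in section 1.2 was not available for this check, so any rationale given there could not be weighed.

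This limits the point but does not remove it. Section 3.4.2 has no Arm 1 exception, and neither the general cadence nor the weekly review produces an on-drug bilirubin.

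Arm 2 has the same empty lead-in and may go to higher doses. The difference is that SX-682 continues there after C1D1, so that panel can still trigger a hold. Table 10 also has no Day -7L draw to build on. A test there is reasonable but optional.

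A further objection concerns the remedy. Replacing participants held for toxicity without a DLT removes some intolerant participants from the 3+3 denominator and can slightly favour escalation. That stands, and the fix allows for it.

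A reader might also infer that single-agent toxicity goes unrecorded or that the DLT count is unreliable. The documents do not support either. Section 6.1 records adverse events from the first dose, the lead-in diary collects side effects, and the C1D1 panel can reveal a laboratory DLT. Nor do they support any claim about how often SX-682 raises bilirubin.

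**Conclusion.** The point holds in a limited form. In Arm 1 there are 28 SX-682 doses and no scheduled blood count or chemistry between the first and the last. The grade 2 bilirubin hold therefore has no scheduled trigger while meaningful dosing remains: nominally 0 doses are left at C1D1, and at most 2 with the window. The gap concerns acting on the hold and seeing transient on-drug changes. It applies to the 9 to 30 participants that section 10.2 expects in Arm 1 (section 3.1.3 implies at least 12).

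The conclusion rests on the calendar as printed and on reading section 3.4.2 as applying to Arm 1, since nothing there exempts it. It does not depend on any assumed toxicity rate. This is an inexpensive improvement in participant safety, not a flaw that undermines the Arm 1 results.

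**What to change.** In section 3.5, add a blood count with differential and a biochemical profile for Arm 1 at Day -7L, drawn with the predose pharmacokinetic sample already in Table 9. State that the result is checked against the hold rules in section 3.4.2.

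Leave the evaluability rule in section 3.1.2 unchanged. It replaces participants who fail to complete the observation period for reasons other than a DLT. A participant who has had a DLT therefore always counts in the 3+3 decision, whatever share of doses was taken. Only a participant held without a DLT who falls below 85% is replaced, and that participant remains in the safety tabulation under section 10.4.5. Because such replacements can lean slightly toward escalation, show these holds to the team at each dose-level decision.

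The cost is extra blood at one existing draw for each of 9 to 30 participants, or a visit or local draw if the pharmacokinetic sample would have been skipped. There may also be a few replacements from the 8 reserve places after holds for bilirubin or other laboratory events, at a rate the documents do not give.
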